All (serious) adverse events or (serious) adverse device effects will be documented on the appropriate “Adverse event/Adverse device effect form.” Safety parameters of this clinical trial are predominantly based on the documentation of adverse events, serious or non-serious, as well as expected and unexpected reactions. Also, near incidents will be reported.

SUBJECT POPULATION AND SAMPLE SIZE

Subjects in the study will be recruited within the UNC School of Dentistry Predoctoral and Graduate clinics. Up to 50 adult subjects (18 years of age and older) will be recruited to provide at least 50 sets of matched or unmatched paired teeth in need of study restorations. Fifty restorations available at baseline and 40 at the 18-month follow-up visit are the minimum number recommended in the 2001 ADA guidelines for clinical trials on resin-based composite resins for posterior restorations. Subjects will be in need of two or four medium-sized Class II restorations in molar and/or premolar teeth.

INCLUSION AND EXCLUSION CRITERIA

To be included in the study, a potential subject must satisfy the criteria described below and be available for the various follow-up visits. A record will be maintained of the reasons for the loss of subjects from the study.

Inclusion Criteria

To be considered for inclusion in the study, subjects must:

- Be older than 18 years of age.
- Have a pair of similar lesions or failed restorations in vital permanent molar or premolar teeth requiring Class II restorations of moderate size that extend between one-quarter and one-third of the way up one or more of the cuspal slopes. Any Class II restoration must have a proximal portion with at least one margin that obviously extends into an interproximal embrasure. (Note: A tooth will be considered vital for the purposes of the study if it is clinically and/or radiographically free of any signs and symptoms of periapical pathology and responds to routine vitality testing.)
- Be capable of giving written informed consent.

Exclusion Criteria

Subjects will be excluded from participating in the study if they:

- Have a history of any adverse reaction to clinical materials of the types to be evaluated.
- Have a medical or dental history that could possibly complicate the provision of the proposed restorations and/or influence the behavior and performance of the restorations in clinical service.
- Have advanced periodontitis affecting the mobility of the teeth.

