- Have xerostomia caused by medications, Sjögren's syndrome, etc.
- Are individuals with special needs.

Distribution of restorations

Each subject shall have a minimum of one pair and a maximum of two pairs of permanent molar or premolar teeth requiring moderate sized Class II restorations. No tooth shall require more than one restoration. Sufficient subjects will be recruited to ensure 50 pairs of test and control study restorations are placed. Although desirable, the pairs are not required to be precisely matched. For example, for purposes of the study, paired restorations can be placed in teeth #15 and #31 (upper left second molar and lower right second molar).

All teeth and restorations in the study will have occlusal contacts. All restorations, with the exception of disto-occlusal restorations in the most distal molars, will have a proximal contact with the adjacent tooth. No two test restorations of either material will be in occlusal or proximal contact with each other.

Selection of Teeth

In addition to the above criteria, the following will apply in tooth selection:

- The tooth must be vital, as determined by thermal test (Hygenic Endo-Ice, Coltène/Whaledent AG).
- The tooth must be of typical size, appearance and morphology.
- The tooth must share, where appropriate, sound proximal contacts with adjacent teeth.
- The tooth must be free of cracks and other defects and lesions necessitating operative intervention other than the restoration to be undertaken as part of the study.
- Proper isolation must be possible.

MATERIALS

The test material is Filtek™ Bulk Fill Posterior Restorative, a bulk fill, low-shrink, light-cured, radiopaque composite resin restorative indicated for use in direct posterior situations. The control material is Filtek™ Supreme Ultra Universal Restorative, a conventional composite resin. Restorations will be bonded with Scotchbond Universal Adhesive.

Manufacturers' instructions for use will be followed for all restoration placements included in the study. Manufacturers' instructions for use for Filtek™ Supreme Ultra Universal Restorative and Filtek™ Bulk Fill Posterior Restorative, and Scotchbond Universal Adhesive are given in the Investigator's Brochure.

PRE-OPERATIVE PROCEDURES

In the screening visit, written informed consent will be obtained from each subject. Each subject will be allowed to ask questions concerning the evaluation and to consider the answers given before signing the consent form.

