The pre-operative status and a periapical radiograph (where clinically indicated) of each tooth to be included in the study will be evaluated and a pre-treatment status form will be completed (Patient Registration Form). The condition of the gingival tissue adjacent to each tooth to be restored will be assessed (four sites: facial, lingual, mesial and distal) and recorded as pre-treatment measurements (Patient Registration Form). Oral hygiene status including plaque index will be determined after periodontal evaluation. Appropriate vitality and radiographic assessments will be completed where indicated clinically, and will be recorded. A pre-operative photographic record will be made.

The restorative material to be used will be allocated by means of a randomization scheme based on computer generated random numbers (Appendix 1). Before starting the study, the PI will decide, by means of a toss of a coin, whether even or odd numbers indicate the test or control treatment. For each set of paired teeth, the lowest numbered tooth (Universal Numbering System) will be selected first. Before cavity preparation, the first randomization number in the sequence will be noted and the allocated treatment procedure carried out as indicated by the random number obtained. The second cavity is then prepared and restored using the second treatment option (next number in the row). Restorative treatments will be randomly assigned to the study teeth at the same visit at which pre-treatment gingival condition, vitality, etc., are determined.

The treating clinician will complete the preparation and placement of restorations, and the arrangements for the subsequent follow-up of the patients.

OPERATIVE PROCEDURES

Local anesthesia will be administered unless declined by the patient. The teeth to be restored will be prepared using conventional instruments and techniques, and no bevels will be placed on any of the cavosurface margins. Shades will be selected before the procedure is started and the tooth is still moist. Rubber dam will be used.

A sectional metal matrix (Garrison Dental or similar) and bitine ring will be placed along with plastic or wooden wedges. At the operator's discretion (e.g., if the preparation is

too wide for a sectional matrix), a thin circumferential metal matrix (Convexi-T, Clinician's Choice or similar) may be used. The bonding system will be used in the selective etch mode according to manufacturer's instructions.

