Restoration placement will be completed in accordance with the recommended procedure for the materials under investigation and in a standardized fashion. After application of the adhesive, a bulk increment (up to 5 mm in thickness) of Filtek™ Bulk Fill Posterior Restorative will be placed and adapted with suitable instruments. Additional increments will be placed as needed. Filtek™ Supreme Ultra Universal Restorative will be incrementally placed in layers (no thicker than 2 mm). The composite resin (each increment of Filtek™ Supreme Ultra Universal Restorative) will be light cured following the recommended exposure time using a device provided by the sponsor. Additional light curing will be performed from facial and lingual for Filtek™ Bulk Fill Posterior Restorative after matrix removal per instructions for use.

Excess material will be removed with suitable instrumentation. Occlusion will be checked and adjusted as needed. Restorations will be polished with diamond abrasives, flexible polishing discs and finishing strips with progressively decreasing grit size (e.g. Sof-Lex™, 3M ESPE), ultra-fine grain diamonds, and/or silicone polishers at the clinicians' discretion. Impressions of restorations using the 3M True Definition Scanner and Imprint™ 3 VPS Impression Material will be taken at each follow-up visit for evaluation of wear over time. Models will be poured and wear determined using the Leinfelder method [18]. The models will also be assessed for wear via optical profiling at the Minnesota Dental Research Center for Biomaterials and Biomechanics. Digital impressions of the restored teeth will be taken at each follow-up visit using the 3M True Definition Scanner. The digital data will be analyzed for wear at 3M ESPE.

The placements and baseline assessments will be completed within 6-12 months of the agreed starting date of the evaluation.

FOLLOW-UP ASSESSMENT

During the follow-up investigation, two examiners will evaluate the restorations relative to the criteria provided by Hickel. The two examiners who undertake the reviews will work independently and will be masked to the treatment conditions. In the event of disagreement between the examiners, agreement will be reached based on discussion. The final result will be marked on the Case Report Form.

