To determine the clinical acceptability of the restoration they are evaluated scoring for their esthetic, functional and biologic properties, which are shown in Table 1. The test requires a sharp explorer plus visual inspection, aided by a mouth mirror as needed. A photographic record will be made of each restoration. For evaluation of marginal adaptation a set of

explorers with different blunt tips of 50, 150 and 250 μm is recommended by Hickel et al. [16]. For assessment of contact point metal strips of different thicknesses of 25 μm , 50 μm and 100 μm can be used. The explorers and metal strips will be provided by the sponsor.

The two masked examiners will use a two-step approach for assigning scores for each parameter. The first step is to assess the restoration and to determine the level of clinical acceptability for each parameter in each of the categories. The result becomes unacceptable whenever re-treatment is necessary.

If a parameter is judged to be acceptable, as a second step, a further distinction can be made between an excellent, good, or clinically satisfactory result. Score 1 means that the quality of the restoration is excellent and fulfils all quality criteria and the tooth and/or surrounding tissues are adequately protected. Score 2 should be selected when the quality of the restoration is still highly acceptable, although one or more criteria deviate from the ideal. The restoration could be modified by polishing and upgraded to an “excellent” rating, but this is not normally necessary. There is no risk of damage to the tooth and/or surrounding tissue. Score 3 means that the quality of the restoration is sufficiently acceptable but with minor shortcomings. Because of their location/extent, however these cannot be eliminated without damage to the tooth, although no adverse effects are anticipated. Scores 1 and 2 would correspond to Ryge’s Alfa rating; Score 3 is equivalent to Bravo.

If a parameter is judged to be unacceptable, a further distinction can be made between a clinically unsatisfactory and clinically poor result. Scores 4 and 5 correspond to Ryge’s Charlie and Delta scoring, which means that a restoration scored 4 is unacceptable but repairable whereas a restoration scored 5 must be replaced [16].

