All restorations carried out in this study will be at no cost to the subjects. Subjects will be expected to attend the one-, two-, three-, and five-year follow up visits. Compensation of \$50 will be paid to each subject at baseline and each follow-up visit (total of \$250).

MONITORING

The study will be monitored at appropriate intervals by [name], Scientific Affairs Manager, 3M ESPE Dental Products, [name] [[contact]], or his designee, by means of regular contact to evaluate study data and photographs.

DATABASE MANAGEMENT

Each subject recruited into the study will be given a unique identifying code number and the subject's identity will be kept confidential as far as is practical.

ANALYSIS OF THE RESULTS

The demographic and baseline measurements, and the study data obtained, will be analyzed by means of tables of percentages to summarize the characteristics of the patients and the baseline data. Tables of percentages will be prepared to illustrate the follow-up and retrospective analysis findings. Cross tabulation will be prepared as necessary.

Statistical analyses

Chi-square (χ^2), McNemar and Mann-Whitney-U tests will be applied as appropriate to compare the baseline and follow-up/review findings regarding the two types of restorations.

PROBLEM CASES

In the case of an experimental Filtek™ Bulk Fill Posterior Restorative or Filtek™ Supreme Ultra Universal Restorative composite resin restoration being found to have failed or to be clinically unsatisfactory on review, the investigator will:

- Complete the failed restoration form.
- Make a photographic and silicone impression record of the failed restoration.
- Make arrangements to replace or, if appropriate, repair the restoration.

Replacements of failed restorations will not form part of the study.

In the case of failure of restorations placed using either restorative system, the tooth will be re-restored at no cost to the subject or investigator. The contact person at 3M ESPE ([name], [contact]) should be notified before this treatment is done.

ADVERSE EVENTS

If an adverse event occurs any decision as to whether to prematurely stop the study will be taken jointly by the PI, 3M ESPE, and IRB. Changes to the protocol will be by arrangement between the PI, IRB, and 3M ESPE, and will take the form of a signed amendment.

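### Test and control restorations share a mouth, but no listed test is paired for the full 1–5 scores, or for wear where the plan's statistics section governs it

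*Combined protocol and SAP*

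**What the plan says.** The design is within-subject. Under SUBJECT POPULATION AND SAMPLE SIZE: "Subjects will be in need of two or four medium-sized Class II restorations in molar and/or premolar teeth". Under Distribution of restorations: "Each subject shall have a minimum of one pair and a maximum of two pairs of permanent molar or premolar teeth", and "Although desirable, the pairs are not required to be precisely matched". PRE-OPERATIVE PROCEDURES randomises the material for the first tooth of a pair and then continues: "The second cavity is then prepared and restored using the second treatment option (next number in the row". The target is 50 pairs.

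The primary endpoint is the FDI rating. FOLLOW-UP ASSESSMENT describes a two-step scoring: "The first step is to assess the restoration and to determine the level of clinical acceptability for each parameter in each of the categories". Acceptable results are then graded 1 to 3 and unacceptable ones 4 or 5. Wear is one of the properties scored in Table 1. It is also measured physically: under OPERATIVE PROCEDURES, impressions "will be taken at each follow-up visit for evaluation of wear over time". Optical profiling of the models goes to an outside laboratory, and of the scans the protocol says "The digital data will be analyzed for wear at 3M ESPE".

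The whole inferential plan is one sentence under Statistical analyses. It names chi-square and then reads "McNemar and Mann-Whitney-U tests will be applied as appropriate to compare the baseline and follow-up/review findings regarding the two types of restorations". No other test or model appears in the document.

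**The concern.** Two restorations in one mouth share the subject's bite, diet, hygiene and caries risk, so their scores may be correlated. A test for independent samples ignores this. Of the three listed tests, only McNemar is paired, and it works on two categories. The qualifier in the sentence lets the analyst choose among the listed tests but does not add one.

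The sentence also leaves open whether McNemar compares the two materials within a pair or compares baseline with review within a material. The gap exists on either reading, because two scores of the same restoration are paired as well.

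At stake are the accuracy of the stated error rate and the precision that a split-mouth design is meant to buy. Direction matters too. The hypothesis is similar performance, with no margin. A test that is too conservative makes a non-significant result more likely, and that result could be read as support for the hypothesis.

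**Working it through.** **1. Data type against listed tests**

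| Data, test vs control in one subject | Chi-square | McNemar | Mann-Whitney U |
|---|---|---|---|
| Acceptable (1–3) vs unacceptable (4–5) | unpaired | paired | – |
| Full 1–5 score | unpaired | only after a two-category cut | unpaired |
| Measured wear | – | only after a two-category cut | unpaired |

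**2. Plan's own figure.** There is none to reproduce. The 50 pairs rest on a guideline minimum, and no alpha, power, effect size, variance or within-mouth correlation is stated. Everything below is therefore assumed: two-sided 5%, a latent shift of 0 or 0.5 SD, and latent within-mouth correlation ρ from 0 to 0.5.

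**3. Direction.** With n pairs and common variance σ², the variance of the difference in means is 2σ²(1−ρ)/n, but an unpaired test uses 2σ²/n. To normal approximation its true size is 2[1−Φ(1.96/√(1−ρ))]:
- ρ = 0.3: 1.96/0.837 = 2.34, size 1.9%.
- ρ = 0.5: 1.96/0.707 = 2.77, size 0.56%.

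This describes continuous wear. Ties in the scores weaken the effect.

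**4. Scores, by simulation.** Latent normal values were cut so that control scores 1/2/3/4 or worse fall in the proportions 60/30/8/2% or 90/8/1.5/0.5%, with 20,000 runs per setting. A repeat run agreed within simulation error.

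True size of Mann-Whitney, 50 pairs, at ρ = 0, 0.3 and 0.5:
- 60/30/8/2: 4.9%, 2.7%, about 1.5%.
- 90/8/1.5/0.5: 5.0%, 3.6%, about 2.4%.

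Power at a 0.5 SD shift, Mann-Whitney vs signed-rank (40 pairs is an illustration of attrition):

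| Setting | ρ = 0 | ρ = 0.3 | ρ = 0.5 |
|---|---|---|---|
| 60/30/8/2, 50 pairs | 0.58 vs 0.56 | 0.59 vs 0.68 | 0.60 vs 0.79 |
| 90/8/1.5/0.5, 50 pairs | 0.37 vs 0.35 | 0.36 vs 0.40 | 0.35 vs 0.47 |
| 60/30/8/2, 40 pairs | 0.49 vs 0.47 | 0.49 vs 0.58 | 0.49 vs 0.69 |
| 90/8/1.5/0.5, 40 pairs | 0.31 vs 0.28 | 0.29 vs 0.32 | 0.28 vs 0.38 |
| Continuous wear, 50 pairs | 0.67 vs 0.67 | 0.70 vs 0.82 | 0.74 vs 0.92 |

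On scores the change is about 0 to −3 points at ρ = 0 (allowing for simulation error), +3 to +9 at 0.3 and +10 to +20 at 0.5.

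**5. How far McNemar fills the gap**
- *Acceptable vs unacceptable.* Exact McNemar needs six discordant pairs, all in one direction: 2 × 0.5⁶ = 0.031, while five give 2 × 0.5⁵ = 0.0625. At an assumed 2% unacceptable in each arm, the expected discordant count at ρ = 0 is 50 × 2 × 0.02 × 0.98 = 1.96. At ρ = 0.3 the joint probability is 0.00166, giving 50 × 2 × (0.02 − 0.00166) = 1.8.
- *Score 1 vs 2 or worse.* At ρ = 0.3, a 0.5 SD shift and 50 pairs there are 21.5 discordant pairs (60/30/8/2) or 11.9 (90/8/1.5/0.5). Power is 0.60 and 0.38 asymptotic, or about 0.50 and 0.29 exact. Signed-rank gives 0.68 and 0.40, and Mann-Whitney 0.59 and 0.36.

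**6. Two pairs per subject.** This case uses 60/30/8/2, ρ = 0.3 and an assumed correlation of 0.3 between a subject's two differences. The unadjusted signed-rank test then has size 5.8% if 10 of 40 subjects give two pairs, and about 7.5% if 25 subjects give all 50. Summing signed ranks by subject gives 4.8% in both. If a subject's two differences are uncorrelated, the unadjusted size is 4.9%.

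**The case against.** A sponsor could answer in five ways.

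*McNemar is paired and is on the list.* This is true, and a reader who infers that the plan has no paired test at all would be wrong. On the cut between score 1 and the rest, asymptotic McNemar nearly matches signed-rank when scores sit near the ceiling (0.38 vs 0.40), and it falls short when they are more spread (0.60 vs 0.68). It would be unfair to judge it only on the acceptable/unacceptable cut, its weakest use. But the plan commits to no cut, so this narrows the point without removing it.

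*Pairs need not be matched.* The wording concerns how alike the teeth are. The protocol's own example of an unmatched pair is still two teeth in one mouth. What stands is that dissimilar teeth may be only weakly correlated.

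*Mann-Whitney does no harm.* A reader might infer that ignoring the pairing inflates false claims of difference. With positive correlation and one pair per subject, the reverse holds. Even in the extreme case of 25 subjects with two pairs each and varying effects, its size was 4.5%. It reached 7.2% only with no shared correlation.

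*Wear may be handled properly elsewhere.* The documents do not say which tests the outside laboratory or the sponsor will use on optical and digital data. They do not support a claim that all wear analysis is unpaired.

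*The loss may be nothing.* This stands. No correlation is given, and at zero correlation signed-rank is slightly worse.

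**Conclusion.** The omission is certain from the text; its cost is not. The size and power figures in the working rest on assumed correlations, score distributions and a 0.5 SD shift. If within-mouth correlation is moderate, the listed rank test runs well below its nominal level and gives up a useful part of a small trial's power. If the correlation is near zero, almost nothing is lost.

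A reader might go further and conclude that the trial is underpowered or its results invalid. The documents support neither. They state no power target, and the error from Mann-Whitney is on the conservative side when correlation is positive. Two pairs per subject are a minor matter: they become important mainly once a paired test is adopted, and only if the material effect varies between subjects. The point should be corrected before analysis, but it does not undermine the design.

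**What to change.** Under Statistical analyses, assign one test to each endpoint for the comparison of materials at each review:

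1. **1–5 scores, and wear analysed under this section:** replace Mann-Whitney and chi-square with a Wilcoxon signed-rank test on test-minus-control differences. Where a subject gives two pairs, rank all pair differences, sum the signed ranks by subject, and take the variance from the subject sums.
2. **Acceptable (1–3) vs unacceptable (4–5):** exact McNemar between materials.

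If baseline-to-review comparisons are also intended, list them separately. State which tests apply to the wear data analysed elsewhere.

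No new data are needed. The downsides are:
- Signed-rank treats score differences as orderable in size. A sign test avoids this but has less power: 0.57 at correlation 0.3 (60/30/8/2, 50 pairs), no better than Mann-Whitney.
- A loss of up to about 3 points of power if correlation is near zero.
- Summing by subject costs little when few subjects give two pairs. With 10 of 40 doing so, correlation 0.3 and no effect variation, power is 0.67, against 0.68 unadjusted and 0.59 for Mann-Whitney.
- In the extreme case of 25 subjects with two pairs each and varying effects, there is no gain: 0.57 vs 0.59 for 60/30/8/2, and 0.31–0.33 vs 0.37 for 90/8/1.5/0.5.
- The change does not by itself establish similar performance, since the plan states no margin.
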